2. PROCEDURES

2.1. General Overview of Procedures

Ionis Pharmaceuticals, Inc. (or designee) will review all study data including source documents, case report forms, and laboratory reports. The study site will enter subject source data into the case report form. Central laboratory data will be transferred electronically from Medpace Reference Laboratories (MRL) Inc. for those analytes noted in the MRL Laboratory Services Agreement, PK Plasma concentration data will be from Pharmaceutical Product Development (PPD) Inc., and immunogenicity data will be from Charles River Laboratories in Montreal (CR-SEN) to Ionis Pharmaceuticals, Inc. Additionally, plasma AGT, Ang II, aldosterone and PRA data analyzed by Attoquant Diagnostics GmbH will be transferred to Ionis via separate Data Transfer Agreement (DTA).

2.2. Randomization & Treatment Allocation

Patients will be randomized after all screening assessments have been completed and after the Investigator has verified that they are eligible per criteria in Clinical Study Protocol Sections 5.1 and 5.2. No subject may begin treatment prior to randomization and assignment of a unique subject identification number.

Eligible patients will be stratified based on a screening eGFR result (< 60 vs. $\ge 60 \text{ mL/min/}1.73 \text{ m}^2$) and then patients will be randomized to 1 of 2 dose cohorts in a 1:1 ratio (Cohort A or Cohort B). Within each dose cohort, patients will be further randomized in a 2:1 to receive ISIS 757456 or placebo as outlined in Clinical Study Protocol Section 4.2. The Sponsor or designee will prepare the randomization list and utilize an automated IRT (Interactive Response Technology) system for randomization assignment.

2.3. Conduct

The study will be conducted in accordance with current Good Clinical Practice (GCP) and International Conference on Harmonization (ICH) guidelines, the World Medical Association Declaration of Helsinki guidelines, the Food and Drug Administration (FDA) Code of Federal Regulations, and all other local regulatory requirements.

2.4. Data Monitoring

2.4.1. Safety Data Monitoring

Ionis Pharmaceuticals, Inc. (or designee) is responsible for processing all reported adverse events (AEs). All serious adverse events (SAEs), reported to Ionis Pharmaceuticals, Inc. (or designee), are reviewed according to standard operating procedures. The medical monitor will review all AEs and SAEs on an ongoing basis throughout the study. Ionis Pharmaceuticals, Inc. (or designee) will prepare and submit safety reports to the health authorities worldwide in accordance with local requirements. If it becomes necessary to communicate new safety information, Ionis Pharmaceuticals, Inc. (or designee) will also prepare a safety notification letter and transmit it to study site.

2.5. Data Management

An electronic case report form (eCRF) utilizing an Electronic Data Capture (EDC) application will be used for this Study.

2.5.1. Case Report Form (CRF) Data

Clario (Formerly BioClinica) (or designee) is responsible for creating the EDC data entry screens, database and edit checks using definitions developed by Ionis Pharmaceuticals, Inc. Ionis Pharmaceuticals, Inc. is responsible for the review, data management querying and locking of the database.

Data are single-entered into the EDC system by the investigator site staff. Programmed edit checks (computer logic that checks the validity of the data entered and also prompts for missing data that is expected to be entered) are run and automatic queries are generated. Ionis Pharmaceuticals, Inc. reviews all data for accuracy and validity and generates additional queries in the EDC system when necessary. The data is corrected or an explanation concerning the query is provided in the EDC system. After all data is entered, source data verified, reviewed and queried the database is closed, the data is then reviewed by Ionis Pharmaceuticals, Inc. and additional queries may be generated if necessary. After all queries are resolved and PI signature are received, the database is locked.

2.5.2. Laboratory Data

Ionis Pharmaceuticals, Inc. is responsible for the format of the laboratory electronic data transfers, the transfer schedule, and the review of the clinical laboratory data. Investigator sites have access to safety data via lab reports sent directly from the laboratory and online using the MRL ClinTrack® database. The laboratory data will be stored as SAS datasets.

Plasma AGT, Ang II, aldosterone, and PRA by Attoquant Diagnostics GmbH will be transferred to Ionis via separate Data Transfer Agreement (DTA).

2.5.3. Pharmacokinetics (PK) and Immunogenicity (IM) Data

Ionis Pharmaceuticals, Inc. is responsible for the management and review of the plasma drug ISIS 757456 concentration data and immunogenicity sample analysis. This review process involves reconciling the patient and visit identifiers (e.g. patient demographics) with the clinical data collected in the EDC system. The final PK data will be stored as CSV and/or EXCEL files per the Analysis Plan.

3. ANALYSIS PLAN

3.1. Statistical Design Summary

This is a Phase 2, randomized, placebo-controlled, multi-center study. Approximated 150 patients will be stratified based on a screening eGFR result ($< 60 \text{ vs.} \ge 60 \text{ mL/min/1.73 m}^2$) and randomized to 1 of 2 dose cohorts in a 1:1 ratio (Cohort A or Cohort B). Within each dose cohort, patients will be further randomized to receive ISIS 757456 or placebo in a 2:1 ratio.

All planned analyses will compare each ISIS 757456 treatment group to pooled Placebo. The overall study type I error is at 0.1 level, two-sided. The multiplicity of study treatment groups comparison and study endpoints testing sequence will be further described in Section 3.4.2.

The planned sample size will provide approximate 80% of power to demonstrate the mean SBP reduction difference of 8 mmHg between each ISIS 757456 treated group and pooled placebo based on the assumption of pooled standard deviation of 13 mmHg with the two-sided test and a significant level of 0.05.

An interim analysis may be conducted after approximately 50% of patients have been enrolled. The unblinding information dissemination during this interim analysis will be controlled and described in the request to unblind data for study analysis document to ensure the trial integrity. Please refer to Section 3.3.2 for further details.

The primary analysis will take place after all patients complete Treatment Period (Day 85) assessments and the database has been locked. The final analysis will be performed after all patients have completed or have had the opportunity to complete the study Day 169 assessments (such as patients who have terminated early) and the database has been locked.

The primary endpoint is the change from baseline to Study Day 85 in seated automated office SBP and will be analyzed by analysis of covariance (ANCOVA) with treatment, randomization stratification factor and baseline measure (SBP) as independent variables. The statistical inferences will be summarized by treatment group. Analyses will assess the hypothesis there are difference in the SBP change from baseline at Day 85 between each ISIS 757456 treatment group and pooled placebo. The estimated treatment effect with 95% CI and p-values will be provided.

Plasma AGT concentration from Attoquant will be used for AGT analysis.

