3. EXPERIMENTAL PLAN

3.1. Study Design

This will be a Phase 2, double-blind, randomized, placebo-controlled study of ISIS 757456 conducted in uncontrolled hypertensive patients on ≥ 3 antihypertensive medications (see Section 5.1 Inclusion Criteria). Patients will be stratified based on Screening eGFR result of < 60 or ≥ 60 mL/min/1.73 m² (see Section 10.1).

The 80 mg and 120 mg once-weekly doses are designed to assess the safety, tolerability, and efficacy of Study Drug (ISIS 757456 or placebo) administered over a 12-week period.

All patients will complete a 13-week Post-Treatment Period.

ISIS 757456 (100 mg/mL) and placebo will be supplied in vials of 0.8 mL in a stoppered glass vial. Study Drug (ISIS 757456 or placebo) injection volumes will be 0.8 mL or 1.2 mL for Cohort A and Cohort B, respectively. All Study Drug injections will be administered by qualified personnel at the clinic or by a Home Healthcare Professional (as arranged with the site staff and after appropriate training). Refer to Section 8.1 for additional details.

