8. TREATMENT OF PATIENTS

8.1. Study Drug Administration

Please refer to the Study Drug Manual provided by the Sponsor for more detailed instructions for Study Drug (ISIS 757456 or placebo) preparation and administration.

Table 4: Study Drug Dosing Information

Cohort	Total Dose
Cohort A	80 mg ISIS 757456 or placebo SC
Cohort B	120 mg ISIS 757456 or placebo SC

^{*} The administration of Study Drug for doses of 120 mg may be delivered as a single injection or 2 non-contiguous injections.

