10.6. Planned Methods of Analysis

All case report form (CRF) data, lab data transfers, and any outcomes derived from the data may be provided in the patient data listings. Patient data listings will be presented for all patients randomized in the study. Descriptive summary statistics including n, mean, median, standard deviation, standard error, interquartile range (25th percentile, 75th percentile), and range (minimum, maximum) for continuous variables, and counts and percentages for categorical variables will be used to summarize most data by treatment group. Where appropriate, p-values will be reported. The placebo patients from both cohorts will be pooled. All primary and secondary endpoints will be assessed on the Full Analysis Set and Per-Protocol Set, with the latter being the basis for the primary efficacy analysis. All safety assessments will be performed on the Safety Set.

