The most conservative approach will be used to determine if the event occurs after the treatment. For example, if the onset date or resolution date of an AE is prior to the first study treatment date, it will be considered to have occurred prior to the study period. If the onset or resolution date of an AE is a partial date with only month or year available or complete missing, then the event is assumed to be within the study period unless the year is prior to the year of the first study treatment date, or if in the same year, the month is prior to the month of the first study treatment date.

Addition summary of hypotension and hyperkalemia incidence will be provided.

Local Cutaneous Reactions at the Injection Site

Local cutaneous reaction at injection site (LCRIS) is defined as (A) moderate or severe adverse events with the PTs Injection site erythema, Injection site swelling, Injection site pruritus, or Injection site pain that started on the day of injection, persisted for at least two days or ongoing; or (B) any AE at the Study Drug injection site, regardless of severity, that leads to discontinuation of study drug, where AE at the Study Drug injection site is the principal reason for discontinuation.

Percentage of injections leading to LCRIS will be calculated as follows for each subject: (A/B)*100, where A = number of injections with an LCRIS, and B = total number of injections. Doses that are split across multiple injections are counted as a single injection

LCRIS will be summarized using the MedDRA coding system, by SOC/PT. Percentage of the injections leading to LCRIS at injection site will also be summarized.

LCRIS will be listed by preferred term.

Flu-like Reactions

Flu-like reactions are defined as adverse events with PTs including either (A) Influenza like illness or (B) Pyrexia or Feeling hot or Body temperature increased, plus at least two of the following symptoms with the PTs: Chills, Myalgia, or Arthralgia, starting on day of injection or the next day.

Percentage of injections leading to flu-like reactions will be summarized using the descriptive statistics.

Percentage of injections leading to flu-like reactions will be calculated as follows for each subject: (A/B)*100, where A = number of injections leading to flu-like reactions, and B = total number of injections.

FLRs will be summarized using the MedDRA coding system by SOC/PT. Percentage of the injections leading to FLRs at injection site will also be summarized.

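### Injection-site reactions are compared with placebo pooled over two injection volumes, which hides the volume-matched placebo data needed to tell volume from drug; the flu-like percentage also lacks a split-dose rule

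*Combined protocol and SAP*

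**What the plan says.** Patients are randomised 1:1 to Cohort A or B and then 2:1 to drug or placebo within the cohort (protocol 4.2; SAP 2.2 and 3.1). Protocol 3.1 ties volume to cohort, for active drug and placebo: "injection volumes will be 0.8 mL or 1.2 mL for Cohort A and Cohort B, respectively". Under Table 4 in protocol 8.1, a footnote adds: "The administration of Study Drug for doses of 120 mg may be delivered as a single injection or 2 non-contiguous injections".

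On the comparator, protocol 10.6 says "The placebo patients from both cohorts will be pooled" and SAP 3.1 says "All planned analyses will compare each ISIS 757456 treatment group to pooled Placebo". SAP 3.7.1 describes exposure for three groups only: placebo, 80 mg and 120 mg. SAP 3.7.2, which covers LCRIS and flu-like reactions, plans no display by cohort, volume or number of injections.

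SAP 3.7.2 defines a per-patient percentage of injections, A/B x 100, for both reaction types. For LCRIS it adds: "Doses that are split across multiple injections are counted as a single injection". For flu-like reactions the definition is "A = number of injections leading to flu-like reactions, and B = total number of injections", with no statement on split doses.

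**The concern.** Pooling placebo is sensible wherever injection volume is irrelevant. Local reactions are the outcome for which volume, or number of injections, could matter without any drug effect. In the active groups volume goes with dose: as randomised, 80 mg means 0.8 mL and 120 mg means 1.2 mL. The design supplies a concurrent, randomised placebo group at each volume, and the planned tables merge the two.

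At stake is how local tolerability is read at the two doses. A volume effect would flatter 80 mg against pooled placebo and count against 120 mg. It could also mask a real drug effect at 80 mg.

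The flu-like percentage raises a separate and smaller issue. The footnote in protocol 8.1 mentions splitting only for the 120 mg dose, so an unstated counting rule would bear on Cohort B and not on Cohort A.

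**Working it through.** The plan gives no local-reaction rate, volume effect or split fraction, so it has no figure of its own to reproduce here. The one design calculation, 43 per group for about 80% power on systolic pressure, does reproduce (two-sample t test, power 0.805), but it does not bear on this point.

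**Group sizes.** 150 x 1/2 = 75 per cohort. Then 75 x 2/3 = 50 active and 75 x 1/3 = 25 placebo, so pooled placebo is 25 at 0.8 mL and 25 at 1.2 mL.

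**Bias from pooling.** Let r be the placebo rate at 0.8 mL, r + d the placebo rate at 1.2 mL, and e80 and e120 the true drug effects in percentage points.
- Pooled placebo: (r + r + d)/2 = r + d/2.
- 80 mg minus pooled: (r + e80) - (r + d/2) = e80 - d/2.
- 120 mg minus pooled: (r + d + e120) - (r + d/2) = e120 + d/2.
- 120 mg minus 80 mg: d + e120 - e80. No placebo term appears, so pooling does not change it.
- Each dose minus its own cohort's placebo: e80 and e120, without bias.

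With no drug effect (all rates assumed):

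| Rate at 0.8 mL | Rate at 1.2 mL | Pooled placebo | 80 mg minus pooled | 120 mg minus pooled |
|---|---|---|---|---|
| 2% | 4% | 3% | -1 | +1 |
| 5% | 10% | 7.5% | -2.5 | +2.5 |
| 5% | 15% | 10% | -5 | +5 |
| 10% | 20% | 15% | -5 | +5 |

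Masking: with placebo rates of 5% and 15% and a true drug effect of 5 points at both doses, 80 mg minus pooled is 10% - 10% = 0, and 120 mg minus pooled is 20% - 10% = 10 points. The matched contrasts are 5 points each.

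**Precision, at an assumed 10% rate throughout.** The 95% half-width of a difference is 1.96 x sqrt(0.09 x (1/n1 + 1/n2)).
- 50 active against 50 pooled placebo: 1.96 x sqrt(0.0036) = 11.8 points.
- 50 active against 25 matched placebo: 1.96 x sqrt(0.0054) = 14.4 points.
- 25 against 25, the two placebo groups: 1.96 x sqrt(0.0072) = 16.6 points.

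**Flu-like percentage.** Take one reaction over 12 doses. Counted by dose, it is 1/12 = 8.3%.
- All doses split (24 injections): 1/24 = 4.2% if A counts one injection per reaction; 2/24 = 8.3% if A counts both.
- Half the doses split (18 injections), A counting both: 2/18 = 11.1% if the reaction followed a split dose; 1/18 = 5.6% if it followed a single injection.

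The timing window in SAP 3.7.2 (the injection day or the day after) fits both injections of a dose split on the same day, so it does not settle what A counts. The effect can be downward, upward or nil.

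**The case against.** The strongest reply is that little turns on this. SAP 3.7.2 names no test for LCRIS or flu-like reactions; they are descriptive summaries and listings. LCRIS is narrow: certain moderate or severe events that start on the injection day and last at least two days or are ongoing, or injection-site events that are the main reason for stopping study drug. Nothing in the documents shows that volume affects its rate, or singles out local tolerability among the safety endpoints; the adverse event of special interest is platelet reduction. Protocol 8.7 also allows weekly dose reductions, so dose and volume are tied by assignment rather than for every injection given. And the example's 5-point bias lies well inside the 14-point half-width of the matched contrast. All of this stands, and it limits the point to a cheap improvement.

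Two stronger readings are tempting and are not supported:
- A reader might infer that pooling manufactures a dose gradient. It does not. The difference between 80 mg and 120 mg is the same whichever placebo column is printed.
- A reader might infer that split doses dilute the flu-like rate and make 120 mg look safer. That needs A to count one injection per reaction, which the SAP does not say, and enough doses to be split, which protocol 8.1 leaves optional. Whether 1.2 mL placebo doses are split is not stated either; if they are, pooled placebo moves too.

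It can also be argued that the LCRIS sentence on split doses carries over to the flu-like formula later in the same section. That is a natural reading, but the text does not say so, and two programmers could differ.

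**Conclusion.** The concern holds in a limited form. For injection-site adverse events and LCRIS, the planned contrast with pooled placebo carries a bias of -d/2 at 80 mg and +d/2 at 120 mg if volume alone shifts the rate by d. This assumes equal placebo numbers per cohort, additive effects and doses given as assigned. The size of d cannot be learned from the documents, and it may be zero. Pooling leaves any gradient between the doses as it is. What it removes is the only randomised evidence on whether such a gradient comes from volume or from drug, and with about 25 placebo patients per cohort that evidence is modest.

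The flu-like issue is an undefined count with no known direction. It does not touch the number of patients with a flu-like reaction, which does not use the injection denominator. Efficacy and sample size are unaffected by either part.

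**What to change.** 1. In SAP 3.7.2, for injection-site adverse events and LCRIS only, add placebo by cohort (0.8 mL and 1.2 mL, about 25 patients each) beside the pooled column. Show each dose against its own cohort's placebo as a descriptive supplement, and keep pooled placebo for efficacy and all other safety tables.
2. In the flu-like paragraph of SAP 3.7.2, apply the LCRIS sentence on split doses to both A and B, so that each counts doses. A full course then has B = 12 in either cohort, whatever the amount of splitting.

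The cost is two table columns and a few lines of SAP text. Trial conduct does not change, and cohort is already recorded through randomisation. The matched contrast is less precise than the pooled one (about 14 against 12 points at an assumed 10% rate), so it should supplement the pooled comparison, not replace it.

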3.2. General Overview of Analyses

3.2.1. Statistical Methods

The study outcomes will be summarized by treatment group. Descriptive summary statistics including number of patients, mean, median, standard deviation, standard error of mean, 25th percentile, 75th percentile, minimum, and maximum for continuous variables, and counts and percentages for categorical variables will be provided to summarize most data. The efficacy endpoints will be assessed on the full analysis set (FAS) and per-protocol set (PPS) with the latter being the basis for the primary efficacy analysis. The safety analyses will be performed on the Safety Set. Pharmacokinetic analysis will be conducted in the PK Set.

All planned analyses will compare each ISIS 757456 treatment group to pooled placebo.

All statistical tests will be conducted using 2-sided tests with 5% Type I error rate unless otherwise stated. P-values will be provided to assess the null hypothesis that there is no statistical difference between an ISIS 757456 treatment group and pooled placebo in study endpoints. The stratification factor (screening eGFR status [<60 vs. ≥ 60 mL/min/1.73 m²]), treatment received, and baseline measure are included in the Analysis of Covariate (ANCOVA) model as independent variables. For the continuous endpoints, the ANCOVA model will be applied or Van Elteren test with treatment and randomization stratification factor if the data departs substantially from normality. The normality assumption will be assessed by the Shapiro-Wilk test based on the residuals from ANCOVA modeling. Least Square mean (LSM) difference with 95% CI and p-values between treatment groups in study endpoints will be provided based on ANCOVA model. For the dichotomous endpoints, logistic regression model with treatment, randomization stratification factor and baseline measure (SBP) as independent variables will be used instead.

To evaluate treatment difference across scheduled post-baseline visits, an additional mixed model with repeated measures (MMRM) analysis may be utilized. Besides stratification factor, visit, treatment received, baseline measure, and treatment-by-visit interaction will be included in the model, which visit as an ordinally categorical variable. An unstructured covariance will be used initially, with correlation coefficients being greater for visits that are closer. Other covariance structures, such as first-order autoregressive covariance structure based on the assumption of the measurements over time are expected to be correlated, may be considered based on model fitting consideration. The adjusted mean with 95% CI for each treatment group and 95% CIs for the mean difference between pooled placebo and each ISIS 757456 treatment groups at each scheduled time point will be provided.

Additional covariates, such as baseline characteristics, may be considered as an additional covariate in the comparison statistical modeling and for subgroup summary for the exploratory analysis purpose.

Laboratory outcomes with lower limit of quantitation (LLQ) or less will be imputed as LLQ in the summary tables and figures.

PK parameters will be summarized using include number of patients, mean, standard deviation, coefficient of variation (CV), geometric mean, median, minimum, and maximum.

Additional subject listings including case report form (CRF) data and derived outcomes from the data may be presented.

Baseline Definition

The baseline for plasma AGT concentration from Attoquant will be defined as the average of all values prior to the first dose of Study Drug. The baseline for all other assessments will be defined as the last non-missing measurement prior to the first dose.

Analytical Visits

In general, all post-baseline data will be summarized using the visit labels provided in the data. Multiple results with the same visit label will be averaged for continuous variables, and the worst result will be used for categorical variables. Results with visit labels as "Unscheduled" will not be included in by-visit summary tables and figures except for determining baseline and the incidence of abnormality lab summary including, but not limited to, AST, ALT, potassium, eGFR, urine protein/creatinine ratio, and platelet specified in Section 3.7.4, but will be presented in data listings. Other situations, such as required additional confirmation, will be described separately in the related endpoint analysis approach.

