10. STATISTICAL CONSIDERATIONS

10.1. Stratification, Subsets, and Covariates

Patients will be stratified on Screening eGFR result of ≤ 60 or ≥ 60 mL/min/1.73 m². In general, the covariates will include stratification factors and baseline measurement.

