3.3. Primary Analysis

3.3.1. Primary Efficacy Analysis

The primary analysis will be the comparison of change from Baseline to Study Day 85 (Study Week 13) in seated automated office SBP between each ISIS 757456 treatment dose group and pooled placebo group in the PPS. The data will be analyzed as described in Section 3.2.1. Least square mean (LSM) estimated treatment difference with 95% CI and p value will be provided. Additional MMRM analysis will be conducted to assess the treatment effect.

Additional covariates, such as baseline characteristics, may be considered, in the comparison statistical modeling for exploratory analyses.

Additional analysis summary based on the FAS will also be provided.

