3.3.2. Sample Size consideration

Approximately 150 patients will be stratified and randomized to 1 of 2 dose cohorts in 1:1 ratio (Cohort A or Cohort B). Within each dose cohort, patients will be further randomized to receive ISIS 757456 or placebo in a 2:1 ratio.

With the assumptions of mean seated automated office SBP reduction difference of 8 mmHg between an ISIS treated group and pooled placebo with the common standard deviation of 13 mmHg, there are at least 86 eligible patients (n = 43 for an ISIS 757456 treated group and n = 43 for pooled placebo) are needed to provide approximate 80% of power to demonstrate the mean difference between an ISIS treated group and pooled placebo by ANCOVA with the two-sided significant level of 0.05. Additional patients are included while considering an estimated approximate 10% drop-out rate.

The overall type I error rate is controlled at 0.1 level, two-sided.

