3.4.2. Multiplicity

The multiplicity of primary and the first three secondary endpoints will be controlled by using sequential (closed) testing strategy in the following testing sequence for interim analysis (if applicable) and final analysis, which is also illustrated in Figure 1 below.

- Comparison of change from baseline to Study Day 85 in in seated automated office SBP between an ISIS 757456-treated group and pooled-placebo in the PPS (primary)
- Comparison of percent change from baseline to Study Day 85 in AGT between an ISIS 757456-treated group and pooled-placebo in the PPS (secondary 1)
- Comparison of change from baseline to Study Day 85 in SBP from 24-hrs mean ABPM between an ISIS 757456-treated group and pooled-placebo in the PPS (secondary 2)
- Comparison of portion of patients reaching the goals of seated automated office SBP ≤ 140 mmHg and DBP ≤ 90 mmHg at Study Day 85 between an ISIS 757456-treated group and pooled-placebo in the PPS, excluding patients with baseline SBP ≤ 140 mmHg (secondary 3)

[figure not shown]

Figure 1: Testing Strategy illustration

In each dose cohort, testing of secondary endpoints will be performed only if the treatment comparison of the primary endpoint is statistically significant. All comparisons between treated group and the pooled placebo for secondary endpoints will be considered as exploratory analyses if the primary endpoint is not statistically significant (p > 0.05, or 0.049 if interim analysis is conducted). If a secondary efficacy endpoint in the sequence is not statistically significant, then the subsequent endpoints outcomes will be considered as exploratory.

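### If residuals look non-normal, the primary SBP test drops the baseline covariate: a valid fallback, but an avoidable loss of efficiency that a rank test keeping baseline would remove

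*Combined protocol and SAP*

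**What the plan says.** SAP 3.1 states that the primary endpoint "will be analyzed by analysis of covariance (ANCOVA) with treatment, randomization stratification factor and baseline measure (SBP) as independent variables". Protocol 10.1 gives the general rule: "In general, the covariates will include stratification factors and baseline measurement".

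SAP 3.2.1 then sets the fallback for outcomes on a continuous scale, as follows: "the ANCOVA model will be applied or Van Elteren test with treatment and randomization stratification factor if the data departs substantially from normality". Its check of normality is this: "The normality assumption will be assessed by the Shapiro-Wilk test based on the residuals from ANCOVA modeling". No cut-off is given for it. SAP 3.3.1 carries this to primary SBP: "The data will be analyzed as described in Section 3.2.1". The logistic model in the same paragraph of 3.2.1 keeps baseline SBP; the Van Elteren fallback does not.

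On reporting, SAP 3.2.1 adds: "Least Square mean (LSM) difference with 95% CI and p-values between treatment groups in study endpoints will be provided based on ANCOVA model". Protocol 10.6.3 says that a nonparametric test is used in place of ANCOVA when normality clearly fails. SAP 3.4.2 sets the threshold for the primary endpoint (0.05, or 0.049 after an interim analysis) but does not name the test that supplies the p-value.

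The SAP revision history for version 2.0 records the move from rank ANCOVA to Van Elteren and gives no reason.

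**The concern.** The endpoint is a change score, so the Van Elteren test does use baseline in that sense. What it loses is the adjustment for baseline as a covariate. Change in blood pressure often depends on the starting value. If it does here, part of the spread in the change score is explained by baseline, and a test that ignores baseline carries that spread as noise.

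The primary result decides, for each dose, whether three secondary endpoints are tested as confirmatory or become exploratory (SAP 3.4.2). A fallback meant to protect the test against non-normal errors could therefore weaken it at the point that matters most.

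**Working it through.** **1. The plan's own figure.** Inputs from SAP 3.3.2: difference 8 mmHg, "with the common standard deviation of 13 mmHg", two-sided 0.05, 43 per group. Noncentrality = 8 / (13 × √(2/43)) = 8 / 2.804 = 2.853. The two-sample t test then has 80.5% power (79.6% with 42 per group), so 43 per group is reproduced.

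**2. What dropping baseline costs when the fallback is the test used.** Take normal errors and a rank efficiency of 0.955.
- Without baseline: 2.853 × √0.955 = 2.788, or 78.7% power at any r.
- With baseline, divide by √(1 − r²). At |r| = 0.6 this is 2.788 / 0.8 = 3.485, or 93.1%. At 0, 0.3 and 0.5 the power is 78.7%, 82.3% and 88.9%.

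With normal errors, however, the switch rarely fires, so the whole rule has to be simulated.

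**3. Whole-rule simulation.** From the SAP: 43 per arm, three arms, effect 8, SD 13 read as the SD of change. Assumed: error shape; r (entered as negative); normal baseline; 30% with eGFR below 60; no stratum effect; Shapiro-Wilk cut-off 0.05 on the three-arm ANCOVA residuals. There were 10,000 trials per cell, and one dose was tested against pooled placebo at 0.05. Power in %, planned rule → same rule with a stratified rank ANCOVA fallback:

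| Errors | Switch fires | r = 0 | 0.3 | 0.5 | 0.6 | ANCOVA alone, 0.6 |
|---|---|---|---|---|---|---|
| Normal | 5% | 80.3 → 80.2 | 83.3 → 83.4 | 89.7 → 90.0 | 93.8 → 94.4 | 94.5 |
| t, 8 df | 34% | 82.6 → 82.4 | 84.2 → 84.9 | 87.3 → 90.3 | 89.6 → 94.1 | 94.0 |
| t, 5 df | 62% | 86.9 → 86.4 | 86.5 → 88.3 | 86.3 → 91.8 | 87.9 → 95.0 | 94.0 |
| Gamma(4) | 98% | 85.8 → 84.9 | 83.6 → 85.9 | 82.5 → 91.0 | 82.0 → 93.8 | 94.2 |
| Exponential | 100% | 96.8 → 96.5 | 94.0 → 95.8 | 89.0 → 96.2 | 86.6 → 97.4 | 93.7 |

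The paired standard error of a difference is at most 0.35 point. With non-normal errors the gains are 0.7 to 2.3 points at 0.3, 3.0 to 8.5 at 0.5 and 4.5 to 11.8 at 0.6. With normal errors they are at most 0.6. At r = 0 the change loses 0.1 to 0.9. At 0.6 the planned rule is below ANCOVA alone in every row.

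A second simulation with independent code (2,500 trials per cell, standard error up to about 0.8 point) gave gains at 0.6 of 8.0 (t, 5 df), 12.5 (gamma) and 11.1 (exponential) points, which agrees within simulation error.

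**4. Type I error per comparison (r = 0, 0.3, 0.6).** Planned rule 4.4 to 5.5%; rank ANCOVA fallback 4.5 to 5.5%.

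**5. Plausible r.** With SBP SD s0 at baseline and s1 at Day 85, and SD of change 13, r = (s1² − s0² − 169) / (26 × s0). The SDs are assumed.
- Equal SDs: r = −13/(2s), which gives −0.65, −0.50 and −0.33 for s = 10, 13 and 20.
- Day 85 SD larger by 3: −100/260 = −0.38, −82/338 = −0.24 and −40/520 = −0.08.

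The documents do not narrow this range.

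**The case against.** The case for leaving the plan alone is substantial.

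- **The test is valid.** Van Elteren on the change score, stratified by the randomization factor, is a sound prespecified test. A reader might infer that the fallback is invalid or leaves the trial underpowered. The figures do not support this: type I error stays near 5%, and power stays at or above about 80%, which is what the design promises. This stands.
- **The choice was deliberate.** Version 2.0 records it, so it cannot be called an oversight. This stands too, although without a stated reason there is nothing to weigh against the loss.
- **No contradiction with the protocol.** A reader might infer that the SAP breaks Protocol 10.1. It does not: that rule is expressly general, and Protocol 10.6.3 asks only for a nonparametric test.
- **The large gains need two things together,** strong correlation and non-normal errors, and the documents establish neither. Screening restricts SBP to above 130 and up to 170 mmHg (Protocol 5.1), which may narrow the baseline spread and pull r toward zero. This limits what can be claimed about size.
- **Which p-value governs is largely settled.** A reader might infer that two p-values are open to choice. Simulated type I error would then be 5.7 to 8.4% with non-normal errors. But Protocol 10.6.3 has the nonparametric test replace ANCOVA, and SAP 3.2.1 offers one or the other, so the inflation belongs to a practice that the documents point away from. The general 5% level in SAP 3.2.1 is also the natural cut-off, though it is not tied to Shapiro-Wilk. What remains is missing detail.
- **Adjusted evidence is still reported,** through the ANCOVA estimate and the MMRM (SAP 3.2.1, 3.3.1). So the question is only which test decides.

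The efficiency point survives: a small worst-case cost against a gain of several points if r is moderate and the switch fires.

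**Conclusion.** The point holds as an avoidable loss of efficiency, not as an error in the plan. After a switch, the test that decides the primary endpoint ignores a baseline value that the protocol and the main model name as a covariate.

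For the whole rule, keeping baseline is worth under about 1 point with normal errors. With non-normal errors it is worth roughly 1 to 3 points at |r| = 0.3 and 4.5 to 12 at |r| = 0.6, against a loss of at most about 1 point at r = 0. At |r| = 0.6 the planned fallback also does worse than never switching. These sizes rest on the assumed error shapes, correlations and 0.05 cut-off, and on reading 13 mmHg as the SD of change before baseline adjustment, which the SAP does not specify. Only SBP was simulated. For plasma AGT, where earlier studies report mean reductions of 54% and 67% (Protocol 2.3.4), the omission is unlikely to matter.

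The change is worth making before unblinding. The cut-off and the governing p-value are accompanying wording.

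**What to change.** In SAP 3.2.1, make the nonparametric fallback for continuous endpoints a stratified rank ANCOVA that keeps the baseline measure: rank change and baseline within eGFR stratum, regress one on the other, and apply a stratified mean-score test to the residuals. Acknowledge in the revision history that this reverses the version 2.0 change.

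In the same edit, before unblinding:
- state the Shapiro-Wilk cut-off, for example p < 0.05;
- confirm in SAP 3.4.2 that the rank ANCOVA p-value replaces the ANCOVA p-value in the testing sequence after a switch;
- say that the ANCOVA LSM difference and CI are still reported but do not decide the sequence in that case.

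The cost is minor SAP wording and a few lines of code, plus up to about 1 point of power if baseline is uncorrelated with change. Baseline is already collected. No protocol amendment appears needed, since Protocol 10.6.3 does not name the nonparametric test and 10.5 leaves the details of the sequence to the SAP.

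Letting ANCOVA always decide is a different trade-off and is not part of this fix. It would need Protocol 10.6.3 changed. At r = 0 it would have 81.5% power against 86.4% (t, 5 df) and 80.8% against 96.5% (exponential) for the rank ANCOVA fallback rule.
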